2.7 Statistical Analysis and Sample Size Justification

The PI, [name], will be responsible for analyzing all study data. The blind will be held at the local site by the VAPAHCS research pharmacist. Once all data has been cleaned and locked, [name] will be unblinded to conduct the final analyses.

Variables/Time Points of Interest

Objective and subjective sleep variables (total sleep time, sleep efficiency, wake after sleep onset, sleep quality) will be collected continuously during the 2-week baseline and the three-week intervention. Subjective alertness assessment will also be collected continuously over the five-week protocol. All of these will be used in the study analyses.

Statistical Methods

The purpose of this study is to test the hypothesis that ingestion of 10 mg of suvorexant 30 minutes prior to daytime sleep initiation in individuals working overnight shifts will significantly improve both objective (total sleep time, sleep efficiency, wake after sleep onset) and subjective (sleep quality) measures of sleep. A secondary goal is to test the hypothesis that ingestion of 10 mg of suvorexant 30 minutes prior to daytime sleep initiation will (1) increase subjective measures of alertness during the night shift and (2) decrease total sleep time during nocturnal sleep episodes on off-days. To accommodate the nested nature of the data (days nested within persons), analyses will be conducted in a multilevel modeling framework (19). Specifically, the total sleep time (TST), as an example, will be modeled as: $TST_{it} = \gamma_{00} + \gamma_{01} * group_i + u_{0i} + e_{it}$, where the TST obtained above for person i on day t , TST_{it} , are modeled separately as a function of between-person and within-person differences. Specifically, γ_{00} , indicates the expected TST score for a prototypical participant on a prototypical day (the reference category); γ_{01} captures between-group differences in sleep (placebo group vs. drug group); and u_{0i} and e_{it} capture additional between-person and occasion-specific differences not otherwise explained. All models will be fit using SAS 9.4 (proc mixed) with restricted maximum likelihood estimation. Effect size will be evaluated with respect to proportional reduction in unexplained variance from an informative baseline model (*pseudo-R²*, see (19)).

Exploratory measures:

While the primary measures in this study will examine *prospective* changes in sleep, we will also collect data that will

examine *retrospective* changes in sleep. These include examining changes in subjective measures of sleep quality that are captured in the BSWSQ, ISI, and FOSQ-10 questionnaires. Changes on these questionnaires will be examined with repeated measure ANOVA. Another exploratory measure to be analyzed in the same manner will be a change in depressive symptom severity as captured on the CES-D. A final exploratory measure will be to examine the change in the number of caffeinated beverages during work shifts. Given that there is tremendous variability in the caffeine content of caffeinated beverages, within subject changes will be examined with multilevel modeling.

Power/Sample Size:

For estimation of sample size, we have reduced our aim to the single, most important outcome measure - will sleep efficiency improve in the drug condition - and reduced the statistical testing to a *t*-test. In previously published work (20), a variance of 3.62% - 3.87% was observed following use of 10 mg of suvorexant or placebo. For purposes of this sample size estimation, we can estimate $\sigma = 5.55\%$ (average variance * 150%, with the increase due to our use of actigraphy instead of polysomnography as a reporter). Setting $\alpha = 0.05$ and power = 80%, we would be able to detect a difference of 5.2% in sleep efficiency (i.e., that which was observed in a previous trial of 10 mg suvorexant in those with insomnia (21)) with 19 participants in each group (n=38 total).

**PROTOCOL
 APPLICATION FORM
 Human Subjects Research
 Stanford University**

Title : A double-blind, placebo-controlled, randomized, parallel design study to examine the effectiveness of 10 mg suvorexant in improving daytime sleep in shift workers

Approval Period: Draft

Protocol Director				
Name [name]		Degree (Program/year if student) PhD		Position, e.g. Assistant Professor, Resident, etc. Asst Professor
Department Psych/Sleep Medicine	Mail Code 5550	Phone [REDACTED]	Fax	E-mail [contact]
CITI Training current				Y

Admin Contact				
Name [name]		Degree (Program/year if student) BS		Position, e.g. Assistant Professor, Resident, etc.
Department Psychiatry and Behavioral Sciences	Mail Code 5550	Phone [REDACTED]	Fax	E-mail [contact]
CITI Training current				Y

Investigator				
Name		Degree (Program/year if student)		Position, e.g. Assistant Professor, Resident, etc.
Department	Mail Code	Phone	Fax	E-mail
CITI Training current				

Other Contact				

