After conclusion of the study, participants would be able to contact their physicians to obtain a prescription for the medication used in this study.

- g) Study Endpoint. What are the guidelines or end points by which you can evaluate the different treatments (i.e. study drug, device, procedure) during the study? If one proves to be clearly more effective than another (or others) during the course of a study, will the study be terminated before the projected total participant population has been enrolled? When will the study end if no important differences are detected?**

The primary endpoint of this study is a change in total sleep time during day time sleep episodes. Given the blinding of the study and the relatively small population being studied, we do not intend to examine the primary outcome prior to study completion (38 total subjects).

3. Background

- a) Describe past experimental and/or clinical findings leading to the formulation of the study.**

The hypocretins (orexins) are a pair of neuropeptides produced by a small group of hypothalamic neurons

Title : A double-blind, placebo-controlled, randomized, parallel design study to examine the effectiveness of 10 mg suvorexant in improving daytime sleep in shift workers
Approval Period: Draft

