While this circadian alerting signal as mediated by hypocretins is indispensable for consolidation of sleep and wake (c.f., sleep and wake fragmentation in those with hypocretin-deficient narcolepsy), it is in direct conflict with obtaining sleep during the daytime, when the circadian alertness signal is working in direct opposition to obtaining sleep. One group of individuals who consistently try to sleep during the biological daytime, when hypocretin-1 concentrations are elevated and opposing sleep, are those who work shifts. According to a survey in 2004 by the U.S. Bureau of Labor Statistics, there are at least 15 million Americans who participate in shift work. While we have the scientific capacity to "flip" the circadian rhythms of individuals working at night and trying to sleep during the daytime, it is a slow process and cannot synchronize individuals who switch between working nights and being awake during the daytime on days off. This leaves two unpalatable options: get poor sleep that is both difficult to initiate and maintain, or take medications such as diphenhydramine (H1 receptor antagonist) or benzodiazepine receptor agonists that induce an artificial and not particularly restful sleep-like state.

Suvorexant provides an ideal solution for improving sleep in shift workers. Histamine H1 receptor antagonists and benzodiazepine receptor agonists force the brain into a state of non-wake. As a dual hypocretin receptor antagonist, suvorexant would suppress the potent circadian drive for wake, thereby creating a permissive state in which natural sleep would be allowed to occur.

b) Describe any animal experimentation and findings leading to the formulation of the study.

see 3a

4. Radioisotopes or Radiation Machines

- a) **List all standard of care procedures using ionizing radiation (radiation dose received by a subject that is considered part of their normal medical care). List all research procedures using ionizing radiation (procedures performed due to participation in this study that is not considered part of their normal medical care). List each potential procedure in the sequence that it would normally occur during the entire study. More Info**

Identify Week/Month of study	Name of Exam	Identify if SOC or Research
------------------------------	--------------	-----------------------------

- b) **For research radioisotope projects, provide the following radiation-related information:**

Identify the radionuclide(s) and chemical form(s).

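### Section 2.7 gives the PI, who is also the analyst, the true treatment codes before the final analyses, while the primary endpoint and baseline handling are unsettled in the visible text; dated choices and A/B codes would reduce the room for steering

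*Combined protocol and SAP*

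**What the plan says.** Three statements in the opening paragraph of section 2.7 set the procedure.

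- On who analyses, the PI "will be responsible for analyzing all study data".
- On custody of the codes, a research pharmacist at the site keeps them, not the PI.
- On timing, unblinding follows lock and precedes analysis: "Once all data has been cleaned and locked, [name] will be unblinded to conduct the final analyses".

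The name in the third sentence is removed. Reading it as the PI is an inference, but the PI is the only person to whom the analysis is assigned. The visible text describes no masked-code stage, no independent statistician and no sign-off of the analysis before the codes are released.

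On what is to be analysed:

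- Application form, section 2 g): "The primary endpoint of this study is a change in total sleep time during day time sleep episodes". The same answer rules out looking at the primary outcome before all 38 participants are complete.
- Section 2.7, Power/Sample Size: the calculation is built on sleep efficiency, which is ranked there as the leading outcome.
- Section 2.7, Statistical Methods: the main hypothesis covers four measures (total sleep time, sleep efficiency, wake after sleep onset, sleep quality). The model is introduced with "Specifically, the total sleep time (TST), as an example, will be modeled as", followed by an equation with an intercept, a group term, a person effect and a residual. It has no baseline or phase term, although two baseline weeks are recorded and are said to enter the analyses.

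**The concern.** A data lock protects the data; it does not protect choices about the analysis that have not yet been made. Under section 2.7 those choices fall to someone who already knows which participants took suvorexant. They include which of two outcomes is primary, whether and how baseline enters, and which participants and sleep episodes count. That person also has a stated expectation: section 3 a) of the application form says "Suvorexant provides an ideal solution for improving sleep in shift workers". No bad faith need be supposed, because a reasonable-looking choice can lean toward the expected answer without intent.

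What is at stake is a directional bias in the estimated effect. The double-blind claim in the title would also cover data collection but not the analysis.

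**Working it through.** **Inputs from the plan (section 2.7, Power/Sample Size).** SD 5.55 points of sleep efficiency, difference 5.2 points, alpha 0.05 (taken as two-sided), power 80%, 19 per group.

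**Step 1: reproduce the plan's figure.** With a two-sample t-test and the noncentral t distribution, 19 per group gives 80.2% power and 18 per group gives 78.0%. The stated 19 per group (38 in total) is reproduced. The present point does not depend on any error in it.

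**Step 2: standard error of the group difference on those inputs.**

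SE = SD × √(2/n) = 5.55 × √(2/19) = 5.55 × 0.3244 = 1.80 points.

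**Step 3: shift when labels are known.** Assume no drug effect and k candidate analyses whose z-statistics have a common correlation r. The analyst always reports the one most favourable to suvorexant. The mean of the reported z is √(1 − r) × m(k), where m(k) is the expected maximum of k independent standard normals: m(2) = 0.564 and m(4) = 1.029. Both k and r are assumptions; the documents give neither.

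| k | r | Shift in SE | Shift in points (× 1.80) |
|---|---|---|---|
| 2 | 0.9 | 0.316 × 0.564 = 0.18 | 0.32 |
| 2 | 0.5 | 0.707 × 0.564 = 0.40 | 0.72 |
| 4 | 0.9 | 0.316 × 1.029 = 0.33 | 0.59 |
| 4 | 0.5 | 0.707 × 1.029 = 0.73 | 1.31 |

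The last column applies only if all candidates are analyses of sleep efficiency, for example with different baseline handling or episode rules. A choice between total sleep time and sleep efficiency mixes units, so there only the SE column has meaning. Relative to the planned 5.2 points, the range runs from 0.32/5.2 = 6% to 1.31/5.2 = 25%.

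**Step 4: shift under A/B codes.** If the analyst picks the largest |z|, the sign of the chosen z is equally likely to favour either arm when the drug does nothing. The mean shift is 0.00.

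**Step 5: does masking lower the false-positive rate?** Null simulation: 200,000 runs, 19 per arm, t-tests, four candidate outcomes. Entries are the chance of a significant result in suvorexant's favour.

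| Correlation | True codes, any favourable outcome taken | A/B codes, smallest p taken |
|---|---|---|
| 0 | 9.6% | 9.2% |
| 0.5 | 7.9% | 7.9% |
| 0.8 | 5.7% | 5.7% |

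One outcome and model fixed in advance gives 2.5%. Masking changes the rate by at most about 0.4 percentage points (9.6 − 9.2); fixing the analysis brings it down to nominal. The two measures therefore do different work: masking removes the direction of the bias, and fixing the analysis removes the selection.

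**The case against.** The case on the other side is substantial.

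*Unblinding after lock is normal.* The blind is held by the pharmacist, lock comes first, and no interim look at the primary outcome is planned. Nothing in the documents claims a masked analysis, so nothing is contradicted. This stands. The sequence matters only because choices are still open when the codes arrive.

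*The choices are less open than they look.* Section 2 g) names one primary endpoint, and section 2.7 says that all listed measures will be used. It also fixes a multilevel framework, software and REML. Presenting the equation as an example most naturally means that the other outcomes get the same one. This stands in part: a reader might infer a free pick among four outcomes, and the documents do not support that. They do leave total sleep time and sleep efficiency competing for first place, and a change endpoint beside a model without baseline.

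*Rules may exist elsewhere.* The text available begins at section 2.7, so episode and missing-day rules may sit in sections not seen. This stands, and the point is limited to the visible text.

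*Masking is weak protection.* With two arms and a directional hypothesis, the analyst may presume that the better-sleeping arm is suvorexant. Sleepiness, which section 9 a) gives as the most common side effect, may also reveal labels. Selection by p-value works equally well under A/B. This stands, and it defeats any claim that masking alone avoids the problem. Guessing from the results is least reliable where protection matters most, however: with no drug effect, the better-looking arm is suvorexant only half the time.

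**Conclusion.** The point holds as a cheap improvement to a stated procedure. It is not an error in any figure and not a breach of the blind. The PI-analyst is unblinded before the final analyses, while the visible text leaves the primary endpoint and baseline handling unsettled.

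The size is directional. Under no drug effect, steering among two to four analyses with labels known moves the estimate toward suvorexant by about 0.2 to 0.7 standard errors, against an average of zero under A/B codes. This assumes correlations of 0.9 to 0.5 and an analyst who always takes the most favourable result, so for each k and r it is an upper limit on steering, not a forecast.

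A reader might infer two stronger things. One is that masked codes would control the false-positive rate. They would not: relabelling the arms leaves |z| unchanged, and the simulated gain is at most about 0.4 percentage points. The other is that the PI's enthusiasm in the background section shows a biased analysis. It shows an expectation, which is a reason for a safeguard and no evidence of misuse.

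**What to change.** Replace the unblinding sentence in section 2.7 with text to this effect:

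> Before any codes are released, the PI dates and files one primary endpoint, the model including baseline handling, the analysis set, and the episode and missing-day rules. After lock, the research pharmacist releases group membership as A/B only. The PI runs and files the primary and secondary analyses under A/B. The pharmacist then reveals the letters, and later analyses are labelled post hoc.

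The first sentence does most of the work, because it closes the choices. The A/B stage is an added safeguard against steering, and filing the output before the reveal stops undisclosed re-analysis afterwards.

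The cost is a short staged release and a filing step. The pharmacist already holds the codes, so no staff are added, and N, alpha and power do not change.

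### Section 2.7 sets a main hypothesis over four sleep measures with no rule for when it is confirmed, and neither of the two single outcomes named elsewhere settles it

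*Combined protocol and SAP*

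**What the plan says.** Three places bear on what decides the trial.

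- **Section 2.7, Statistical Methods.** The purpose is to test that the drug "will significantly improve both objective (total sleep time, sleep efficiency, wake after sleep onset) and subjective (sleep quality) measures of sleep". Two further hypotheses, on night-shift alertness and on off-day nocturnal sleep, are labelled secondary. A multilevel model is written out for total sleep time as an example, which implies one model per outcome. No significance level, testing order, multiplicity adjustment or any/all rule is given.
- **Section 2.7, Power/Sample Size.** For estimating the sample size only, "we have reduced our aim to the single, most important outcome measure - will sleep efficiency improve in the drug condition", and the authors "reduced the statistical testing to a *t*-test". The only alpha in the documents is here: "Setting $\alpha = 0.05$ and power = 80%, we would be able to detect a difference of 5.2% in sleep efficiency", with 19 per group.
- **Protocol Application Form, section 2(g), Study Endpoint.** "The primary endpoint of this study is a change in total sleep time during day time sleep episodes".

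**The concern.** The documents give three answers to the question of which result decides the trial: four measures jointly, sleep efficiency, or total sleep time. The reduction to one outcome is made for the sample size and is not carried into Statistical Methods. Choosing one primary outcome would still leave the four-measure hypothesis in 2.7, with no stated status for the other three.

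Two things are at stake. If one significant result among the four may be reported as support, the error rate for the main claim exceeds that of a single test. If the claim is read literally as objective *and* subjective improvement, the quoted 80% belongs to a different and easier claim. In addition, the three objective measures are largely re-expressions of the same actigraphy record, so three significant results among them would not be three independent confirmations.

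**Working it through.** **Inputs from the documents.** Difference 5.2 and SD 5.55 for sleep efficiency, alpha 0.05, 19 per group (2.7, Power/Sample Size). Four measures in the main hypothesis (2.7, Statistical Methods).

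**Not in the documents, so assumed.** Two-sided tests; 0.05 for each model-based test; the correlations between measures; effects and SDs for total sleep time, wake after sleep onset and sleep quality. The check uses *t*-tests, as the sample-size paragraph does, not the planned multilevel model.

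**Step 1: reproduce the plan's figure.** Noncentrality = 5.2 / (5.55 × √(2/19)) = 2.89 on 36 degrees of freedom, critical value 2.028. Power is 80.2%, so 19 per group reproduces. A one-sided test would need only 15, so the plan's figure fits a two-sided test. It covers sleep efficiency alone.

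**Step 2: closed-form figures under independence.**

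- At least one of four significant, either direction: 1 − 0.95⁴ = 18.5%.
- At least one of four significant in the drug's favour: 1 − 0.975⁴ = 9.6%, against 2.5% for one test.
- One pre-named objective measure and sleep quality, 80% power each: 0.8² = 64%.
- All four, 80% power each: 0.8⁴ = 41%.

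**Step 3: allow correlation.** The second to fourth rows simulate *t*-tests with 19 per arm and a standardised effect of 5.2/5.55 on every measure (100,000 trials per row). The last two rows use a normal approximation with 80% power on each measure.

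| Correlation: among objective / objective with sleep quality | Any of four, no effect, either direction | Same, drug's favour | Power: named objective + sleep quality | Power: all four |
|---|---|---|---|---|
| 0 / 0 | 18.5% | 9.6% | 64% | 41% |
| 0.5 / 0.2 | 16.6% | 8.5% | 66% | 52% |
| 0.7 / 0.2 | 15.2% | 7.7% | 66% | 55% |
| 0.9 / 0.4 | 12.3% | 6.1% | 68% | 62% |
| 0.8 / 0.8 | 11.4% | 5.7% | 73% | 66% |
| 0.9 / 0.9 | 9.4% | 4.7% | 75% | 70% |

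The first four rows give the ranges 12-19%, 6-10%, 64-68% and 41-62%. The last two require self-reported quality to track actigraphy as closely as the actigraphy measures track each other.

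**Step 4: sensitivity of the joint power.** With sleep quality at 50% power, the others at 80% and a common correlation of 0.5, all-four power is 40%. With 90% power on each, it is 66-81% for common correlations 0 to 0.8. If any one of the three objective measures sufficed alongside sleep quality, power lies between 70% and 80%; the 64-68% is for an objective measure named in advance.

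**The case against.** The strongest reply is that a single primary outcome already exists. If section 2(g) governs, the one confirmatory test is on total sleep time; if the sample-size paragraph governs, it is on sleep efficiency. Either way there is one test at 5%, the other measures are supportive, and nothing is inflated. This reply would succeed if the two places agreed. They name different outcomes, and neither is carried into Statistical Methods. The reply does show that the lack of a decision rule is tied to the primary-outcome conflict, so both should be settled in one edit.

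Other points on that side stand:

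- 0.05 for each model-based test is an inference. The level is stated only for the sample size.
- The either-direction rate overstates the specific harm, because only results favouring the drug could be reported as support. The relevant comparison is about 6-10% against 2.5%.
- The joint power depends on effects and SDs that the documents do not give.
- This is a single-site study of 38 completers, declared in the drug section of the form as not intended to support a new indication. That limits the consequences but does not supply the rule.

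A reader might also add the two secondary outcomes and quote a six-test error rate. The documents do not support that: 2.7 puts alertness and off-day sleep in a separate secondary tier, and a result on either could not confirm the main sleep hypothesis.

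**Conclusion.** The concern holds as a missing decision rule combined with conflicting single outcomes. The error and power figures are alternatives, one for each reading:

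- **Any one of four counts:** about 12-19% chance of a false positive in either direction, about 6-10% in the drug's favour. This assumes two-sided 0.05 for each test, objective correlations 0-0.9 and objective-subjective correlations 0-0.4. The rates fall to 9.4% and 4.7% if all four correlate at 0.9.
- **The literal *both* claim:** no such inflation, since requiring every named test to succeed needs no alpha adjustment. Power is about 64-68% for one pre-named objective measure plus sleep quality and about 41-62% for all four, if each measure had 80%. The documents support 80% for sleep efficiency only.

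A reader might infer that the plan demands significance on all four and also carries a 12-19% error rate. These cannot both be true. Nor do the documents establish any particular joint power: they establish only that the stated 80% was not calculated for the joint claim. The change should be made, but it does not call the trial's feasibility into question.

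**What to change.** Reconcile Statistical Methods, Power/Sample Size and section 2(g) to one primary outcome. Then add a fixed sequence to 2.7. Each step is a single test at two-sided 0.05 and is formal only if the previous one is significant:

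1. the primary outcome that the sponsor keeps;
2. sleep quality (steps 1 and 2 together form the objective-and-subjective claim);
3. the first of the two remaining objective measures, in a stated order;
4. the second of them;
5. and 6. the two secondary outcomes, in a stated order.

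Report every estimate with a 95% confidence interval whatever the sequence yields. State that the 80% power was calculated for sleep efficiency alone and applies neither to total sleep time nor to the joint claim. Give any joint power only as a range with its assumptions.

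The cost is wording, with no extra participants. The downside is that later outcomes lose a formal claim if an earlier test fails, and the order after step 2 is the sponsor's judgement. The alternatives cost more. Bonferroni at 0.05/4 = 0.0125 leaves 60% power for sleep efficiency at 19 per group and needs 28 for 80%. Powering all four jointly at 80% would need about 24-29 per group (normal approximation, equal standardised effects, common correlation 0.8 to 0). The edit should be final before the data are unblinded, because 2.7 has the principal investigator run the analyses after unblinding.

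### The stated model for the sleep outcomes does not use the two-week baseline and does not say which days are analysed

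*Combined protocol and SAP*

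**What the plan says.** Under Variables/Time Points of Interest, section 2.7 says that the objective and subjective sleep variables "will be collected continuously during the 2-week baseline and the three-week intervention". It adds "Subjective alertness assessment will also be collected continuously over the five-week protocol", and then "All of these will be used in the study analyses".

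Under Statistical Methods there is one equation, with total sleep time (TST) as the example: TST_it = γ00 + γ01·group_i + u0i + e_it. The coefficient γ01 "captures between-group differences in sleep (placebo group vs. drug group". The rows are described only by "where the TST obtained above for person i on day t". No other model is given for a primary or secondary outcome.

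Other places that bear on the point:

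- The application form, section 2a, makes weeks 1-2 monitoring only. Pills are taken in weeks 3-5.
- Section 2g of the form defines the primary endpoint as a change in daytime total sleep time. The Exploratory measures text in 2.7 begins "While the primary measures in this study will examine *prospective* changes in sleep".
- One secondary hypothesis is that the drug will "decrease total sleep time during nocturnal sleep episodes on off-days".
- Under Power/Sample Size, a t-test with 19 per group is the basis for "we would be able to detect a difference of 5.2% in sleep efficiency".

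**The concern.** The endpoint is described as a change, and two weeks of baseline are collected on every participant, yet no term in the model expresses a change or uses the baseline. The equation also leaves open which days supply the rows, and the two readings have different consequences.

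- **Weeks 3-5 only.** The group coefficient is a valid randomised comparison and matches the sample-size t-test. However, chance baseline differences between two groups of 19 stay in the estimate, and precision that the data could supply is given up.
- **All five weeks.** The coefficient averages untreated days, where the expected difference is zero, with treated days. The estimate is pulled toward zero and power falls well below the plan's 80%.

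The type of sleep episode matters too. The hypotheses predict longer total sleep time by day and shorter total sleep time on off-day nights. The hypotheses name these episode types, but the equation indexes only person and day.

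**Working it through.** **Inputs from the plan (2.7, Power/Sample Size):** difference 5.2 points of sleep efficiency, SD 5.55, α 0.05 (two-sided reproduces the plan), 19 per group. **Assumed:** ρ, the correlation between a participant's baseline mean and treatment-period mean, taken as 0.3 to 0.7 (to 0.9 for pooling), with the same SD of 5.55 at baseline. The documents give neither.

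**1. The plan's figure.** Two-sample t-test, noncentral t, 36 df: 19 per group gives power 80.2%, so the stated size reproduces. The 95% CI half-width is 2.028 × 5.55 × √(2/19) = 3.65 points. This is also the weeks 3-5 result without a covariate. With equal rows per person, the group coefficient of the random-intercept model equals the difference between arms in person means. Fitting the written model by REML to 8 simulated data sets (38 people, 20 rows each) confirmed this to four decimals, with t statistics agreeing within 0.0002.

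**2. Weeks 3-5 with the baseline mean as covariate.** Residual SD = 5.55 × √(1 − ρ²).

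| ρ | Residual SD | Power, closed form | Power, 35 df and covariate penalty | Mean half-width, simulated |
|---|---|---|---|---|
| 0.3 | 5.29 | 83.8% | 82.7% | 3.51 |
| 0.5 | 4.81 | 90.1% | 89.2% | 3.19 |
| 0.7 | 3.96 | 97.6% | 97.2% | 2.63 |

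Simulated power (100,000 trials per ρ) was 82.8%, 89.2% and 97.2%.

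**3. Baseline imbalance left in the estimate.** The SD of the difference in baseline means is 5.55 × √(2/19) = 1.80 points. Without the covariate, a 1-SD chance imbalance moves the estimate by ρ × 1.80: 0.54 points at ρ = 0.3 and 1.26 at ρ = 0.7.

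**4. All five weeks.** At the minimum of four night shifts a week (application form, 8h) there are 8 untreated and 12 treated daytime sleeps, so the treated share is w = 12/20 = 0.60. The coefficient targets 0.60 × 5.2 = 3.12 points. SD = 5.55 × √((1−w)² + w² + 2w(1−w)ρ).

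| w | ρ = 0.3 | ρ = 0.5 | ρ = 0.7 | ρ = 0.9 |
|---|---|---|---|---|
| 0.55 | 48% | 43% | 39% | 35% |
| 0.60 | 54% | 49% | 45% | 41% |
| 0.65 | 60% | 55% | 50% | 46% |

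The outer shares allow for lost days: 10/(8+10) = 0.56 and 12/(6.5+12) = 0.65. At w = 0.60, 80% power would need 34, 39, 44 and 49 per group.

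**5. Change score,** if the word change is meant literally. SD = 5.55 × √(2(1−ρ)). Power is 66%, 80% and 95% at ρ = 0.3, 0.5 and 0.7, below the covariate model each time.

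**6. Leaving the choice open.** With no true effect, taking the smaller p-value of the weeks 3-5 and five-week analyses rejects in 7.4%, 6.8%, 6.5% and 5.8% of simulated trials at ρ = 0.3, 0.5, 0.7 and 0.9.

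**The case against.** The large loss of power needs baseline days to be outcome rows, and the text supports that only weakly. The sentence saying that everything will be used follows a list of variables, and using a variable does not make untreated days outcomes. The hypothesis concerns sleep after taking the drug, which happens only in weeks 3-5. The equation is labelled an example and refers back to total sleep time obtained above, and the text available for review does not include what came before section 2.7. The 6-7% false-positive rate also presumes that an analyst would pick the smaller p-value, which nothing suggests. All of this stands, so the five-week figures are conditional and the case does not rest on them.

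On the weeks 3-5 reading, chance imbalance is not bias, because the unadjusted interval already allows for it. The gain also depends on ρ. It is under 3 percentage points at ρ = 0.3 and about nil at 0.2 (80.7%), and at 0.1 there is a slight loss (79.5%). This is correct. It limits the size of the gain, but the covariate remains a sensible choice because its downside is so small.

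Two phrases might seem to answer the concern, but they do not. The informative baseline model in Statistical Methods is a reference for pseudo-R², not an adjustment for baseline weeks. Repeated-measures ANOVA and within-subject change are planned only for exploratory measures.

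Finally, an off-day nocturnal baseline is sparse: at four shifts a week it is at most about 2 × 3 = 6 nights. That is a practical detail for the fix to cover.

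**Conclusion.** The concern holds and should be fixed, although it does not make the trial invalid. On the reading most favourable to the plan, the analysis is sound but leaves an already collected baseline unused. Using it would raise power for sleep efficiency from 80% to about 83%, 89% or 97% at ρ = 0.3, 0.5 or 0.7. On the five-week reading, which the text permits but does not compel, the effect estimated falls to 55-65% of the true one, and power is 35% to 60% across the shares and correlations tried.

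These figures rest on an assumed ρ, an equal baseline SD and roughly equal numbers of rows per person. They apply to sleep efficiency. For total sleep time, the endpoint named in section 2g, the documents give no SD or effect, so only the 55-65% share carries over. Unblinding after data lock is ordinary practice. The point is only that rows and covariate should be written down before it.

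**What to change.** Before unblinding, state in section 2.7:

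1. For daytime total sleep time, sleep efficiency, wake after sleep onset and sleep quality, the outcome rows are daytime sleep episodes in weeks 3-5.
2. The model is Y_it = γ00 + γ01·group_i + γ02·baseline_mean_i + u0i + e_it, where the baseline mean is the participant's mean of the same measure over daytime episodes in weeks 1-2. The test is of γ01.
3. Night-shift alertness uses the same form, with rows from night shifts in weeks 3-5 and the weeks 1-2 night-shift mean as covariate.
4. Off-day nocturnal total sleep time uses the same form, with rows from off-day nocturnal episodes in weeks 3-5 and the weeks 1-2 off-day nocturnal mean as covariate.

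Add a line on how a missing or very sparse baseline mean is handled, so that participants do not drop out of the model. The covariate form is preferable to a change score because its power is higher at each correlation examined.

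The cost is SAP wording and one model degree of freedom. No extra data, visits or participants are needed.
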